## **9.8 Suspension of research**

An adverse event where the patient has an unexpected reaction to the drug will suspend this study. An example of such an event would be a seizure or a drastic increase in pain in the limb after administration of a single dose of the active drug. One other way to stop the trial is by an objection by a member of the data safety monitoring board, which exists to monitor all adverse events in this trial.

# **10.0 Risks**

## Loss of confidentiality:

One potential risk is the possible consequences of breach of confidentiality.

## Venipuncture:

There is a venipuncture risk drawing blood of a slight pinch or pin prick when the sterile needle enters the skin. The risks include mild discomfort and/or bruising at the site of the puncture. Less common risks include a small blood clot, infection or bleeding at the puncture site, and on rare occasions fainting during the procedure.

## 4-AP study drug:

In addition, serious risks associated with allergic reaction to the study medicine including shortness of breath or trouble breathing, swelling of the throat or tongue or hives are possible. There is also a serious risk of kidney or bladder infection and seizure.

The following information will be included in the consent form to make sure that the subjects understand the risks:

- The research participant could have a seizure even if they never had a seizure before.

- The chance of having a seizure is higher if too much study medication is taken or if the participant's kidneys have a mild decrease of function, which is common after age 50.
- The participant's kidneys will be checked before start of study medication to determine how well they are working.
- Before taking study medication, the participant should tell the doctor if they have kidney problems.

The study medication can also cause dizziness, confusion and balance problems. Therefore, prior to leaving the CRC, patients planning on driving or operating machinery, should be familiar with how the study medication affects them.

Risks of EDX tests: The EDX tests that will be performed are low-risk procedures, and complications are rare. There's a small risk of pain (although rarely encountered), bleeding, infection and nerve injury where a needle electrode is inserted.

The member of the study team trained to conduct the EMG will need to know if the participant has certain medical conditions. The participant must tell the study team member and other EMG lab personnel if the subject:

- Has a pacemaker or any other electrical medical device
- Takes blood-thinning medications
- Has hemophilia, a blood-clotting disorder that causes prolonged bleeding

Risks of Randomization: The primary risk of randomization is that the treatment the subjects receive may prove to be less effective or to have more side effects than the other study treatment(s) or other available treatments. A secondary risk of randomization is that the randomization process is somehow in error, and the patient is assigned to the wrong group. This would result in a patient exposed to treatment and labelled as having been exposed to placebo. The only negative effect of this error would be to mask the truly beneficial effects of the treatment. The same masking would occur if a patient assigned to treatment, being given instead placebo. This would have the same masking effect. Neither effect exposes patients in this trial to harm.

### **Protection Against Risks**

Breaches of confidentiality will be reduced by storing the data on secure share drives within Penn States Trial Data Center (part of the Department of Public Health Sciences). Access will be restricted to the investigators, the study coordinator, and any agency legally empowered to demand access to the data and only encrypted, password-protected computers will be used.

Potential risks and discomforts from taking the study medication will be minimized to the greatest extent possible by closely monitoring subjects for the most common side effects including allergic reactions and the less common side effect of seizure while in the CRC and after discharge (see above). Study subjects will be asked by study personnel after the CRC day about any potential symptoms and any evidence of difficulty or adverse event will be evaluated.

Estimated glomerular filtration rate (GFR) is assessed prior to inclusion in this study and in trauma patients as standard of care and will be known before initiating the trial with 4-AP. In patients with mild renal impairment (estimated GFR 51-80 mL/min), 4-AP plasma levels may approach those seen at a dose of 15 mg twice daily, a dose that may be associated with an increased risk of seizures. As mild renal impairment is common after age 50, estimating GFR is particularly important in these subjects. Patients with renal impairment (estimated GFR≤80 mL/min) will be excluded from the study based on the fact that this level of impairment is contraindicated in the use of 4-AP.

4-AP has never been shown to definitively exacerbate renal function in humans and studies in animals only reveal alterations at doses several-fold higher than are used in our proposed study. The relationship between 4AP dosage and

estimated GFR levels is based on the importance of renal function in removing 4-AP from the system. Therefore, the risk of 4-AP use in this patient population is directly linked to the risk of changes in estimated GFR. To be on the safe side of renal clearance issues, however, we have taken two specific steps with regards to issues with 4-AP in renal toxicity. First, we have excluded patients with estimated GFR  $\leq 80$  mL/min based on the fact that this level of impairment is contraindicated in the use of the study drug. This criteria means that we even have excluded patients whose estimated GFR levels actually met criteria for inclusion in earlier 4-AP trials. Second, we are using lower doses of 4-AP in this study than were used in initial studies for 4-AP for a variety of neurological maladies to further ensure we do not run into toxicity issues. The specific dose we have selected is the starting dose used in multiple sclerosis patients prior to dose escalation.

Randomization errors are protected against in this trial by double checking the randomization protocol in IDS and use of redcap. Further checking and oversight is planned at the DSMB level prior to initiating the trial and after the 80% mark is achieved.

## **11.0 Potential Benefits to Subjects and Others**

### **11.1 Potential Benefits to Subjects**

A known risk in nerve injury is a delay in recovery of function attributable to inability to correctly diagnose a nerve laceration without EDX, which only becomes sensitive to the continuity of the nerve weeks after the injury. It is well known that early surgical exploration and repair of lacerations of the nerve is best in patients with known nerve lacerations and detrimental for patients found at surgery to have an unsevered nerve. As this trial offers no change in the overall standard of care for nerve patients other than a trial of a drug to see if it returns function or sensation (clear indications that the nerve is not severed), this trial does not alter the standard of care for these patients. The benefits are a clear indication of the status of the nerve weeks before the gold standard test can reveal the same information – but this benefit is only realized in the drug group and only if return of function is demonstrated. 4-AP is a known neuro-enhancing agent we hypothesize will potentially return function transiently but long enough to reveal those patients whose nerves are intact but not working. Furthermore, we predict this diagnostic intervention will also limit the difficulty and stigma associated with not knowing if their nerve has been cut, again a direct benefit only realized when continuity is demonstrated. This trial only affects patient decisions to pursue further treatment if return of function is clearly demonstrated. Otherwise, patients might have no return of function either because their nerve was indeed severed in the trauma or if they received placebo. As such, no direct conclusions or alterations in patient care will be based on these results for trial patients. Also, since there are additional research visits included at two week intervals in this trial, recovery will be followed with greater accuracy over time.

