### 1.2 Primary Study Endpoints

Primary Aim and Study Endpoint: Return of voluntary function and subjective sensation not present after trauma.

**Summary of Specific Aims:** This proposal contains two distinct aims to be investigated in two similar but distinct groups of patients. This will be measured by sensory, motor and sudomotor (electrical conduction tests), and electrodiagnositc (EDX) testing.

**Aim 1:** To examine the mechanistic effect of 4AP on the return of sensorimotor function and EDX sensitivity in the setting of nerve dysfunction from orthopaedic trauma. This aim tests the hypothesis that oral one-time administration of 4AP provides transient return of function and EDX sensitivity to the traumatically denervated limb in alert patients with known limb injuries not involving the central nervous system.

**Aim 2:** To examine the mechanistic effect of 4AP on the return of sensorimotor function and EDX sensitivity in the setting of iatrogenic nerve injury after surgical intervention. This aim tests the identical hypothesis as in Aim 1 in a distinct group of patients, whose nerve dysfunction is the result of a clinical intervention, and whose function before that intervention was intact.

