## 7.2. 1 Visit 1 in Clinical Research Center (CRC) and/or Inpatient setting~8 hours

**Trial Logistics and Organizing framework:** Patients for this trial are divided into two aims. Patients enrolled for one aim, are excluded from the other aim, because the causes of the injury, which define the aim, are exclusive. Aim 1 is for post traumatic neuropathy. Aim 2 is for post surgical or post intervention neuropathy. Within each aim, there are treated patients and placebo patients. Only one patient will be evaluated at a time. Evaluation takes one day. Patients will be randomized in the Penn State University Clinical Research Center (CRC) or at the bedside, where they will stay for a period of analysis afterwards that lasts a few hours.

[figure not shown]
Eligible, consented patients will present for testing from one of three locations (emergency department, inpatient ward, or home). Patients will undergo testing in the CRC and/or bedside under the direction of trial personnel. Testing will be initiated by patients undergoing a thorough sensory and motor evaluation and establishing an intravenous line for blood sampling. A baseline blood sample and EDX study (prior to drug or placebo) and sensorimotor examination will be performed. These tests comprise part of a standardized array of tests performed hourly. This array of tests (serum 4AP level, EDX study, and sensorimotor examination) will be repeated every hour after treatment for five hours (Figure 1) during which the drug will have decreased to a level low enough to have no expected effect. The final hourly test is the return to baseline test. It is likely going to occur at the fifth hourly posttest, but is depicted separately for clarity. Only five tests after dosing will be necessary, based on our expectations from known pharmacokinetic data.

Finally, testing is concluded at the end of this period. Research subjects will be provided a diary and asked to record symptoms as instructed. The subjects will be asked to maintain the diary for 20 weeks and the diaries will be reviewed at each follow up visit and collected at or after the final 20 week visit.

[figure not shown]

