## **12.0 Sharing Results with Subjects**

The results of this study include both subjective and objective measures. It is impossible to hide the subjective measures from the patients given the nature of our measurements. We will prevent active discussion of objective measures until final follow up at 20 weeks. Patients will be free to use their subjective assessments of the return of function in their standard-of-care treatment decisions. We will not inform other physicians except at the express consent of patients to do so. Subjective responses to treatment can be discussed, again at the patient's request, with treating physicians before final follow up. Objective test results will not be discussed with treating physicians until 20 weeks, again, only with patient consent to do so. In cases where the patient's decision to seek further surgical exploration of an injured peripheral nerve based on subjective return of function (or lack of return) seems ill-advised to members of the study team, a patient conference will be arranged in conjunction with the ethicist and DSB. Such cases where the patient intends to monitor a nerve where our subjective findings suggest clear evidence that the nerve requires surgical exploration, are expected to be rare. Other such cases, where the patient intends to elect for surgical exploration of a nerve which is believed, based on the results of the study, to be in continuity, may be slightly more common. In both of these cases, the patient's decision in conjunction with the treating surgeon (who is purposefully excluded from the study team to avoid any conflicts) is held to be paramount. Conferences of the type described above will be held in selected cases where the evidence from the trial is deemed to be clearly in conflict with the decision taken by the patient – only to ensure adequate education, again with prior consultation with the DSB. Unblinding will be discussed at this time as well.

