**Patient Source:** Patients will come from two sources. The first will be traumatized patients presenting with nerve dysfunction. These patients often have concomitant orthopaedic injuries, which require stabilization. If the nerve was dysfunctional before intervention, then the patient will be included as a recruit for aim 1. The second source is patients who suffer nerve dysfunction after a surgery or intervention where nerve injury may not have been expected, as is the case with routine fracture fixation or joint arthroplasty procedures. In such cases, post-intervention examination may reveal a loss of nerve function where the continuity of the nerve again cannot be established. These patients, owing to their intact nerve function before the intervention, will be included as recruits to aim 2. In point of fact, both groups of patients have the same phenotypic condition, namely the loss of nerve function where the continuity of the nerve is not demonstrable. However, they are grouped into differing aims because the latter group suffers nerve dysfunction as the result of an intervention or surgical procedure and critically, these patients will have a clear pre-intervention examination without any nerve dysfunction.

Splitting aims is necessary because of the differing means by which the patient is injured and the different circumstances of injury. Surgeons will often tell patients who would qualify for aim 2 that they are absolutely sure that the nerve is not severed, altering the pre-test/pre-trial likelihood that the patient may feel a return of function even if exposed to the placebo. We therefore intend to keep the recruitment and counselling of aim 2 patients separate from those who present after traumatic, non-iatrogenic nerve injury.

**Patient Selection and Availability Patient Availability and Cohort Query Analytics:** Ambiguous nerve continuity is common in our medical center. Initial estimates, based on stakeholder provider interviews,

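### A self-reported return cannot by itself show continuity in a blinded patient, so sections 11.1 and 12.0 need reconciling with the placebo returns that 15.2 accepts

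*Combined protocol and SAP*

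**What the plan says.** Section 1.2 sets the primary endpoint as "Return of voluntary function and subjective sensation not present after trauma", so a patient's own report of feeling is part of it. No responder threshold is given. Under 7.2.1 the test array "will be repeated every hour after treatment for five hours".

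Section 11.1 describes a trial of a drug to see if it "returns function or sensation (clear indications that the nerve is not severed". It adds that "this benefit is only realized in the drug group and only if return of function is demonstrated", and names placebo only as an explanation for a negative result: "patients might have no return of function either because their nerve was indeed severed in the trauma or if they received placebo".

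Section 15.2, explaining why aim 2 is kept separate, says that surgeons often assure these patients the nerve is whole. This changes the likelihood that "the patient may feel a return of function even if exposed to the placebo".

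Section 12.0 then says: "Patients will be free to use their subjective assessments of the return of function in their standard-of-care treatment decisions". It also foresees patients who "elect for surgical exploration of a nerve which is believed, based on the results of the study, to be in continuity", and provides for a conference in selected cases of conflict, at which unblinding is discussed.

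**The concern.** If a return can be felt on an inert capsule, a felt return does not depend on conduction restored by the drug. Neither the patient nor the study team knows the allocation, so neither can tell an expectation-driven return from a drug-revealed one. A return that rests on self-report alone therefore cannot establish continuity in that patient. Sections 11.1 and 12.0 contain no such caution.

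This concerns positive results only; 11.1 already explains that a negative result is ambiguous. It matters because 11.1 itself says that early repair is best for a nerve known to be lacerated. A patient with a severed nerve who reports feeling something could be falsely reassured during the weeks before electrodiagnostic testing becomes informative. The wording also credits a positive result with more diagnostic certainty than the design can supply for one person.

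**Working it through.** **Figures in the plan.** There are none on this point to reproduce. The protocol gives no false-return rate, no expected placebo return, no proportion of severed nerves (8.3 says only that severance is less likely in aim 2) and no specificity. Section 8.2 declines to give a sample-size basis.

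**Step 1: the passages side by side.**

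| Section | Position on return |
|---|---|
| 11.1 | A return is a clear sign of an unsevered nerve; placebo explains only a lack of return |
| 15.2 | A return may be felt on placebo (aim 2) |
| 12.0 | Patients may use a subjective return in decisions; the team may believe in continuity from study results |

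**Step 2: the logic.** Let p be the probability that a patient reports a return for reasons other than drug-restored conduction. The description in 11.1 is exact for a self-report only if p = 0. Section 15.2 implies p > 0, at least in aim 2. A severed nerve can then be accompanied by a reported return, in either arm.

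**Step 3: illustration.** Every input here is an assumption: 1:1 allocation; the same p in both arms and for both nerve states; drug response r = 0.7 in continuous nerves and none in severed nerves; proportion severed s.

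- P(return | continuous) = 0.5[p + (1 − p)r] + 0.5p
- P(return | severed) = p
- P(severed | return) = sp / [sp + (1 − s)P(return | continuous)]

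For p = 0.2, P(return | continuous) = 0.5 × 0.76 + 0.5 × 0.2 = 0.48, so the likelihood ratio for continuity is 0.48/0.2 = 2.4. With s = 0.2, P(severed | return) = 0.04/(0.04 + 0.384) = 9.4%.

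| p | Likelihood ratio | P(severed given return), s = 20% |
|---|---|---|
| 5% | 7.7 | 3.2% |
| 10% | 4.2 | 5.7% |
| 20% | 2.4 | 9.4% |
| 30% | 1.8 | 12.1% |

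With s = 10%, the last column runs from 1.4% to 5.8%. At p = 20% and s = 10%, the placebo arm supplies 0.10/(0.02 + 0.432) = 22% of all returns.

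A simpler version sets the total return rate t in continuous nerves on drug, so that P(return | continuous) = 0.5t + 0.5p. With t from 50% to 80%, p from 5% to 20% and s from 5% to 30%, P(severed | return) runs from 0.6% to 19.7%. In both versions it is zero when p is zero.

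**Step 4: repeated testing.** There are five post-dose tests. If a false report has chance f at each test and the tests are independent, the chance of at least one is 1 − (1 − f)^5. This is 4.9%, 9.6%, 22.6% and 41.0% for f = 1%, 2%, 5% and 10%. Under full dependence it stays at f.

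**Step 5: number of patients.** In the 50 patients of 8.1, the expected number with a severed nerve and a reported return is 50sp. This runs from 50 × 0.05 × 0.05 = 0.125 to 50 × 0.30 × 0.20 = 3.0.

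**The case against.** Four points on the other side carry weight.

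- A reader might infer that 11.1 claims a return is seen only on drug. It does not. It confines the benefit to the drug group, and only where return is demonstrated. That can be true alongside placebo returns and may stay. What does not stand is calling a return a clear sign of an unsevered nerve without allowing for a report made on placebo.
- A reader might infer that the plan has a rule classifying any self-reported return as proven continuity. No section contains one. Section 11.1 is a statement of benefits, and the planned comparison in 8.3 is drug against placebo, which controls for expectation at group level. The gap is in the reading of the individual result.
- Safeguards exist. Section 7.2 weights objective over subjective sensory tests 2:1 and uses two independent observers of movement; 19.1.2 adds dual assessment; 7.2.2 schedules electrodiagnostic testing at 6, 12 and 18 weeks. Under 12.0 the choice rests with the patient and a treating surgeon outside the study team. None of these defines a return or estimates how often false ones occur. Apart from medical emergencies (18.6), unblinding is raised only at the selected conferences.
- Section 11.1 disclaims any conclusion or change of care resting on the results. It also says, however, that a clearly demonstrated return does affect patients' decisions, and 12.0 permits that use.

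It is also fair that 15.2 speaks of aim 2, where 8.3 considers severance less likely. Yet 8.3 says that dysfunction in those patients cannot be told apart from cases later found severed, and 11.1 covers both aims.

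**Conclusion.** The point holds as an inconsistency between 11.1, 12.0 and 15.2 that can falsely reassure an individual patient. While allocation is blinded, a return resting on self-report alone is evidence about continuity but does not settle it. In the illustration, with 20% severed beforehand, a return lowers the probability of severance to between 3.2% and 12.1%. That is informative, but it is not a clear indication.

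The true size is unknown. All rates used are assumptions, and the single p applied to both arms and both nerve states may not suit aim 1 and aim 2 equally. The documents do not support the stronger inferences that a known share of severed nerves will be misread, or that the drug-placebo comparison itself is invalidated.

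**What to change.** Reconcile 11.1, 12.0 and 15.2 as follows.

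- **11.1:** replace the description of a return as a clear indication. Say instead that it is the hypothesised sign of continuity under test, and that a reported return can also occur on placebo. The statement that drug-revealed benefit arises only in the drug group may stay.
- **12.0:** state that a self-reported return may occur on placebo and is not conclusive for the individual while allocation is blinded.
- **8.3:** use self-reported return in the drug-placebo comparison, and report the placebo-arm return rate beside it, by aim and with a confidence interval. The interval will be wide. With 25 patients in an aim (3.3.2) and 1:1 allocation assumed, about 12 receive placebo. Even no returns in 12 leaves a one-sided 95% upper limit of 1 − 0.05^(1/12) = 22%.

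Which observations establish continuity, and how clinicians act on them, is for the sponsor to settle; no such rule is proposed here. The change needs wording in two sections and one reporting line, with no new tests. The small downside is that the stated benefit to subjects becomes slightly less favourable.
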